After pile sorting, the second activity during the interview will be a user experience design session⁸⁴, an area that Co-I [name] has expertise in from his work designing health communication tools and decision aids. This process, which draws on techniques used in design thinking, prioritizes consulting with prospective users early and often, and will help the study team to better incorporate patient perspectives in the design of the final appointment reminder messages. In the design session, we will present participants with: a) a status quo appointment reminder letter; and b) draft intervention appointment reminder letters. After identifying the changes with highlighting, we will query participants about how each message is perceived, interpreted, and comprehended. Questions will also specifically probe about potential harms (e.g. feelings of guilt) and the principles we are trying to evoke (e.g., social norms).

Iterative design process: We will begin with a wave of six interviews (pile sort + design session). After each wave of design sessions, we will construct a spreadsheet compiling participants' feedback for each draft message. This spreadsheet will function similarly to a codebook—facilitating identification of themes in participants' interpretations of the messages. The research team will collectively review these responses to make consensus decisions about revisions to the interventions. Members of the Veteran Engagement Group (VEG) at our HSR&D Center to Improve Veteran Involvement in Care (CIVIC) will also participate in selected design meetings to offer additional Veteran-centered input. Depending on whether messages map onto our proposed BE and Theory of Planned Behavior concepts and how messages are perceived, the team may change wording in messages, delete messages, or develop multiple message versions to test in the next wave. We will continue these six-interview waves until we reach stable intervention content. Because the design process is iterative, a final sample size cannot be pre-specified, although based on experience we expect to

conduct at minimum of three waves (18+ interviews). Six or more waves are possible. Interviews will last approximately one hour, and be audio-recorded to facilitate accurate capture of all relevant comments.

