Aim 1: Develop and iteratively refine BE-informed messages based on Veterans' perceptions, and incorporate them into enhanced appointment reminders.

Hypothesis: Perceptions of messages will be consistent with our conceptual framework and not associated with emotional harms.

Aim 2: Determine the effect of four versions of enhanced appointment reminders on measures relevant to treatment access, compared with usual reminders.

Hypotheses: 1. Each intervention group will have a lower no-show rate, as compared with usual care. 2. Each intervention group will have a higher advanced cancellation rate, as compared with usual care. Exploratory

Hypothesis: Wait time will be shorter in intervention groups than with usual care.

Aim 3: Evaluate differences in treatment effect associated with four versions of enhanced appointment reminders.

Hypothesis: Effect size of nudges will vary by intervention arm such that some types of nudges will have a larger proportional effect than others.

Aim 4: Characterize potential barriers and facilitators to widespread implementation of enhanced appointment reminder messages. We will conduct semi-structured interviews with key informants (10 Veterans locally and 30 VHA staff nationally). Interview guides will be informed by selected domains and constructs from the Consolidated Framework for Implementation Research.

SCIENTIFIC RATIONALE AND SIGNIFICANCE

BACKGROUND

Why are no-shows a critical health services issue now?

[figure not shown]
Providing and maintaining patient access to care has been declared by leadership as the Veterans Health Administration's (VHA) highest priority. Deficits in access have been shown to contribute to decreased patient satisfaction³⁷, higher mortality rates³⁸ and diminished quality of care³⁹. Amidst an environment of limited access and long wait times, VHA is simultaneously struggling with "no-shows."

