No-shows are defined as scheduled appointments that are neither attended nor canceled, and represent a "missed opportunity" on several levels. First, for patients, no-shows may contribute to reduced access and increased wait time. A VA Office of Inspector General audit noted that "reducing unused outpatient appointments could improve timeliness of Veterans' patient care"⁷. Another report found that inefficiencies caused by no-shows in VHA make it "difficult to meet the performance measure of seeing new patients within 30 days"⁴⁰. Second, no-shows contribute to inefficient use of healthcare resources. No-shows result in appointment slots that unexpectedly go unused; further, after a no-show, clinics frequently spend time re-scheduling. The same Office of Inspector General audit estimated that suggested that reducing no-shows in could allow VHA facilities to more efficiently use millions of dollars each year⁷. Third, no-shows represent a missed clinical opportunity. The appointment was scheduled for a clinical reason, which does not get addressed when there is a no-show. Many vulnerable, at-risk groups, including psychiatric patients, ethnic minorities, and low-income patients are disproportionately impacted by no-shows^{4,41,42}, which can contribute to further disparities in clinical outcomes and quality of care^{4,41}.

Why are current approaches to address no-shows in VHA inadequate?

VHA struggles with elevated no show-rates, which have not improved in recent years. VHA's overall no-show rate continues to be approximately 13-14%, far above Secretary Shulkin's stated goal of five percent. In FY2015 this rate led to a total of over nine million no-shows. Despite VHA efforts aimed at reducing no-shows, such as recall scheduling and new patient orientation clinics, no-show rates have been static for years, according to VHA Support Service Center (VSSC) data (see **Figure 1**)¹⁵.

Figure 1. National VA No-Show Rates Between 2013 and 2016

What Veterans are likely to no-show and why?

Research led by our operational partner [name] has described some common characteristics of Veterans who miss visits: mental health and rehabilitation are the service lines with the highest no-show rates; no-show rate increases with age of the appointment (i.e., how long ago it was scheduled); new patients have higher no-show rates; male Veterans have somewhat higher no-show rates than females until age 65, after which it equalizes².

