The National Initiative to Reduce Missed Opportunities was a large VHA project that established many of the reasons for and risk factors related to no-shows, and their results reinforce the importance of appointment reminders. One of their national surveys (n=4,749) determined that forgetting was the most frequent reason (19%) cited by Veterans for a no-show⁸. In contrast, issues that would not be addressed by reminders (e.g., poor weather, sickness, and transportation issues) were much less common reason for no-shows (all cited by <8% of Veterans). Furthermore, Veterans who received a reminder letter, postcard, or call were significantly more likely to remember their appointment (85%) than those who did not receive a reminder (75%).

Why use appointment reminder systems and mailed letters or postcards to address access issues?

Appointment reminders are a key ingredient to promoting appointment attendance and cancellation of appointments that are no longer needed. (In this proposal, we use the term “**appointment reminder**” to refer to either reminders sent before an appointment or messages sent after a no-show.) Decades of research has definitively established the efficacy of appointment reminders in reducing no-show rates^{11,14,43} and recent trials have suggested that appointment reminders can trigger more patients to cancel, rather than no-show, presumably because they no longer feel the appointment is necessary^{31,44}.

No-shows are not simply limited to a small group of outlier patients. Our preliminary data compiled from VSSC show that 40% of unique patients in mental health clinics, and 15% in primary care, had at least one no-show in VA Portland Health Care System (VAPORHCS) in 2016.

Appointment reminders letters and cards will continue to play an essential role in VHA. [name], MHA, former National Project Manager of the National Initiative to Reduce Missed Opportunities (NIRMO) at the VA Pittsburgh Healthcare System's Veterans Engineering Resource Center (VERC) noted that appointment reminders are "not going away" despite an evolving access landscape. In addition, VA Directive 1230, released recently on July 15, 2016, reinforces the use of multiple appointment reminders as standard practice in mental health.

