By examining different types of nudges in different intervention arms, this project will help advance scientific understanding of the mechanisms behind behavior change related to appointment attendance. If successful, it would also lay the groundwork for a subsequent study where we would have the resources to conduct full factorial testing, identify optimal combinations of messages/nudges, and determine whether synergistic effects can be achieved by combining messages. **Table 2** contains a more detailed description of what kinds of messages fall into each of the four categories of nudges. For most of the four concepts, multiple draft messages are presented.

Table 2: Messages included in the appointment reminder based on the related concept

Concept	Message
Caring	We're here for you.
Consequences for Others	Call now so we can help another Veteran in need.
Consequences for Self	Attending appointments lowers your chances of being hospitalized.
Consequences for Self	If you miss your appointment, you may have to wait a while to be seen.
Social Norms	Most Veterans make a point to attend their VA appointments. If they can't make their appointments, most Veterans also make an effort to let us know.
Behavioral Instructions	Need to change or cancel your appointment? Take these 2 simple steps today: 1) Call the clinic at [contact]. 2) Give your name, last 4, and appointment information. It's fine to leave a message.

Intervention 1 (Social Norms + Behavioral Instructions): A letter with two types of nudges. One points out the common behavior of attending appointments. And one provides clear, specific instructions for making appointment changes. The appointment reminder also includes usual care (basic appointment information on date, location, and phone number(s) for scheduling changes).

Research has shown that social norms messages have a positive impact on behavioral action, however it is not clear how effective it is in comparison to messages framed around consequences. Additionally, we did not use the caring message in this intervention arm to allow for comparison of whether the caring message on its own has a positive impact.

Intervention 2 (Caring + Consequences for Others + Behavioral Instructions): A letter with three types of nudges. One suggests that the institution cares about the patient. One highlights a potential negative consequence for others if the patient no-shows. And one provides clear, specific instructions for making appointment changes.

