Our primary outcome will be no-show rate, or the proportion of total appointments that are classified as a no-show, relative to the total number of appointments scheduled. The numerator (“no-shows”) consists of appointments marked as a no-show and appointments canceled by the patient or clinic after the appointment time. The denominator (“total appointments”) consists of no-shows and completed appointments. No-show rates will be measured at the provider-level.

Table 3. Trial Outcomes (Aims 2 & 3)

Outcome	Measure	Data Source
Primary	No-show rate	CDW
Secondary	Cancellation rate	CDW
	Advance cancellation rate	CDW
	Patient-initiated cancellation rate	CDW
Exploratory	Raw wait time	CDW
	Clinically indicated wait time	CDW
	Waiting room time	SHEP
	New mental health appointment wait time	CDW

Our secondary outcome will be cancellation rate, defined as the proportion of scheduled appointments that are marked as canceled. In addition to overall cancellation rate, we will also determine the rate amongst the subset of cancellations that are advance cancellations and patient-initiated cancellations. Advance cancellations, defined here as at least five days before appointment, provide a metric with a reasonable window of time (informed by preliminary data provided by our schedulers) that allows the opportunity to fill a cancelled slot with another waiting Veteran. Patient-initiated cancellations provide a more specific indication of intervention effects on cancellation behavior. Cancellation rates will be measured at the provider-level.

Finally, as exploratory outcomes, we will calculate wait time and number of unique patients seen per day. The latter is simply the number of daily completed encounters, adjusting for patients who have multiple encounters in the same day. For wait time, we will use multiple validated metrics:

- Raw wait time is defined as the length of time in days between the date an appointment was created and the date the appointment was completed⁷⁴. If an appointment is cancelled or a no-show, the wait time will be calculated based on the next appointment that is scheduled and completed in the same clinic stop code.

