effectiveness of interventions varies. For example, we will explore whether the effect of the interventions differ between men and women. To analyze our exploratory outcomes on appointment wait time, we will evaluate time-to-completed appointment using an extended multivariate Cox regression model to account for multiple appointments at the patient level and clustering at the provider level.

Aim 2 Hypotheses: To address Hypothesis 1 (Each intervention group will have a lower no-show rate, as compared with usual care) and Hypothesis 2 (Each intervention group will have a higher cancellation rate, as compared with usual care), we will conduct pairwise comparisons to test for differences between the interventions and usual care as $H_0: \beta_j=0$ for Interventions $j=1,2,3,4$.

Aim 3 Hypothesis (Effect size of nudges will vary by intervention arm such that some categories of nudges have a larger proportional effect than others): We will conduct pairwise comparisons of no-show and cancellation rates by testing the linear combinations between each of the four intervention arms (e.g., Intervention 1 and Intervention 2; $H_0: \beta_1=\beta_2$).

Aim 4: ATLAS.ti software will be used for data management. We will employ a “rapid assessment process,” which is useful for quickly developing understanding from an insider’s perspective and informing future implementation efforts^{81,92}. This multi-step process will be as follows: 1) create domain names for each interview question; 2) create and test a summary template; 3) summarize interview transcripts using the summary template, and 4) transfer summaries into a matrix (respondent x domain) data display⁹³. Our summary template will consist of domains and constructs from our interview guides (i.e., CFIR), and we will compose a templated summary for each interview. We will review these summaries on a regular basis (approximately every five interviews) to ensure interviews build iteratively on emergent findings.

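### A higher cancellation rate counts as a favourable result in Aim 2, but no primary or secondary outcome counts completed care, so both hypotheses could be met while fewer visits take place

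*Combined protocol and SAP*

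**What the plan says.** Hypothesis 2 of Aim 2 is that "Each intervention group will have a higher advanced cancellation rate, as compared with usual care". J. Data Analysis restates it for cancellations in general: "Each intervention group will have a higher cancellation rate, as compared with usual care". Under either wording an increase is the hoped-for result.

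Two reasons are given for welcoming cancellations. The Background says that reminded patients may cancel rather than fail to appear, "presumably because they no longer feel the appointment is necessary". Section I. Measures adds that a slot freed five or more days ahead can go to another waiting Veteran.

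The Background also names the patient-level harm of a missed visit: "The appointment was scheduled for a clinical reason, which does not get addressed when there is a no-show".

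Table 3 lists the no-show rate as primary and three cancellation rates as secondary. The text of section I defines the primary denominator as no-shows plus completed visits. The wait-time measures are exploratory. One of them, raw wait time, handles the cancelled appointment: "If an appointment is cancelled or a no-show, the wait time will be calculated based on the next appointment that is scheduled and completed". The later visit has to carry the same stop code. For its analysis, "we will evaluate time-to-completed appointment using an extended multivariate Cox regression model to account for multiple appointments at the patient level", with clustering by provider. The number of unique patients seen per day is named in the text of section I but not in Table 3.

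**The concern.** If a missed visit matters because a clinical need goes unmet, a cancelled visit that is never made up leaves the same need unmet. The plan presumes that the visit was no longer needed, or values the freed slot. The first is not tested by any primary or secondary outcome. The second benefits a different patient.

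The primary outcome does not protect against this, because a visit cancelled in advance leaves both its numerator and its denominator. An arm could lower the no-show rate partly by removing appointments from the count, and the same cancellations would support Hypothesis 2.

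The pilot in Preliminary Studies reported attendance as well as no-shows (a 3.8% increase beside a 0.6% decrease). The trial's outcome table has no attendance measure. What is at stake is whether a favourable Aim 2 result can be read as better access to care.

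**Working it through.** The plan states no figure on this point, so there is none to reproduce. The check asks which mixtures of extra cancellations move both hypotheses the favourable way.

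**Inputs**
- No-show rate 13.5%: midpoint of the 13–14% VHA figure in the Background.
- Extra cancellations 2.7 points: the larger difference assumed in K. Power Analyses for no-show and cancellation rates.
- Baseline cancellation rate 20%, range 10–30%: an assumption, because the documents give none.

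**Baseline per 1,000 scheduled:** cancelled 200; remaining 800; no-shows 0.135 × 800 = 108; completed 692.

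**Add 27 cancellations.** The remainder is 800 − 27 = 773. No-show rate = remaining no-shows / 773. Cancellation rate = 227 / 1,000 = 22.7% in every row.

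| Source of the 27 | No-shows | Completed | No-show rate | Range at 10% to 30% baseline cancellation |
|---|---|---|---|---|
| All would-be no-shows | 81 | 692 | 10.5% | 10.8% to 10.0% |
| Half and half | 94.5 | 678.5 | 12.2% | 12.4% to 12.0% |
| In proportion | 104.4 | 668.6 | 13.5% | 13.5% |
| All would-be attenders | 108 | 665 | 14.0% | 13.9% to 14.0% |

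In the half-and-half row both results look favourable and 692 − 678.5 = 13.5 original visits are lost.

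**General condition.** If a share s of t extra cancellations comes from would-be no-shows, the new rate is (108 − s·t) / (800 − t). This is below 108/800 whenever s exceeds 13.5%. So the no-show rate can fall even when most extra cancellations come from people who would have attended.

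**A full 2.7-point fall in the no-show rate.** Setting the new rate to 10.8%, with a share a of the extra cancellations from would-be attenders, gives t = (108 − 0.108 × 800) / ((1 − a) − 0.108).
- a = 25%: t = 21.6 / 0.642 = 33.6 extra cancellations and 0.25 × 33.6 = 8.4 visits lost.
- a = 50%: t = 21.6 / 0.392 = 55.1 extra cancellations and 0.5 × 55.1 = 27.6 visits lost.

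**Other denominator.** The opening sentence of the primary outcome definition refers to all scheduled appointments. On that basis the half-and-half row still looks favourable: 108/1,000 = 10.8% falls to 94.5/1,000 = 9.45%.

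**Scale.** Four of five equal arms: 0.8 × (102,060 + 157,587) = 207,718 scheduled appointments a year; × 0.027 = 5,608 extra cancellations. Mental health alone: 0.8 × 102,060 × 0.027 = 2,204.

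**Does raw wait time fill the gap?** It follows the patient, but three things are unstated:
- The value for someone with no later completed visit.
- Whether the clock runs from the original creation date or from that of the next appointment. If it restarts, the delay caused by the cancellation disappears even for patients who return.
- The censoring time in the Cox model.

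Unique patients seen per day counts whoever was seen, including those who fill freed slots, so it cannot show what happened to the patient who cancelled.

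**The case against.** The strongest reply is that the plan already follows these patients. Raw wait time runs on to "the wait time will be calculated based on the next appointment that is scheduled and completed in the same clinic stop code", the Cox model makes completion the event, and B. Data Source allows extraction for two years after study completion. Patients who do not return would lower an arm's hazard. This stands against a reading that a reader might infer, namely that no outcome follows the patient who cancelled. That reading is wrong. What remains is that this outcome is exploratory and incompletely defined, and that no rule links the reading of cancellations to it.

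A reader might also infer that lost care is bound to be reported as benefit. The table does not support that. If only would-be attenders cancel, the primary outcome worsens to 14.0%. If only would-be no-shows cancel, no original visit is lost. Only a mixture misleads.

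Nor does the loss have to be large. If both rates moved by exactly the plan's 2.7 points, completed visits would be 773 × (1 − 0.108) = 689.5 against 692 per 1,000. At 10% baseline cancellation there would be no loss (873 × 0.892 = 778.7 against 778.5). At 30% it would be 5.2 (673 × 0.892 = 600.3 against 605.5). For the same reason, turning the roughly 5,600 extra cancellations into a yearly number of lost visits is not supported: the documents give no non-return rate, and such a figure would give no credit for averted no-shows.

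It is also tempting to say that the letters push attenders to cancel. The current letter already asks patients to telephone if they cannot come. The message "Call now so we can help another Veteran in need" appears only in letters that also explain how to change or cancel a visit. The documents do not show which patients would respond. Finally, a favourable result would not lead straight to system-wide use, since L. Limitations and Alternatives foresees a further multi-site trial.

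**Conclusion.** The point holds as a cheap improvement. Aim 2 counts more cancellations as success, the primary rate drops advance cancellations from its denominator, and nothing at primary or secondary level measures completed care. A favourable result on both hypotheses is therefore compatible with fewer completed visits.

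The illustration gives 13.5 fewer original visits kept per 1,000 scheduled, with a no-show rate of 12.2% and cancellation of 22.7%. It rests on an assumed 20% baseline cancellation rate, the 13.5% no-show midpoint and an assumed even split. The direction of the two results does not change across baseline cancellation of 10–30%. The 1.3-point fall in the no-show rate there is smaller than either difference in K. Power Analyses, so it would not always be declared significant. The plan's figures support about 5,600 extra cancellations a year at a 2.7-point difference, about 2,200 of them in mental health. The net effect on completed care is unknown, which is the reason to measure it.

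**What to change.** Add to Table 3 a secondary outcome from CDW, by arm and separately for mental health and primary care, with all eligible scheduled appointments as the denominator:

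- (a) the proportion completed as scheduled;
- (b) the proportion whose patient completes a visit in the same specialty within a fixed, pre-stated window after the original date, an attended original visit counting as met. Ninety days is one option; it is not taken from the documents.

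Analyse both with the planned mixed model. Report the difference from usual care, with its confidence interval, beside the cancellation result, and interpret a higher cancellation rate as improved access only in light of that interval. Do not use a pass/fail test that the proportion is not lower. No margin is defined, and section K reports only 80% power in mental health for 2.7 points against usual care, so such a test would turn largely on noise.

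Any return rate among cancelled or missed appointments should be descriptive only, because it conditions on an event after randomisation that the letters are meant to change.

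For the time-to-completed-appointment model, state the clock start, the handling of patients with no later completed visit, and the censoring time.

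The cost is wording in the analysis plan and derived variables from dates, stop codes and appointment outcomes that B. Data Source and section I already extract. Extraction for two years after completion leaves room for a full window for every appointment. The downside is one more outcome and a more qualified cancellation claim.
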